14.4.2 Sample Size Considerations and Statistical Methods for Primary Retention Measure

If a participant did not complete 12 weeks of treatment, time of drop-out from substance abuse treatment will be recorded. If a participant completes all 12 weeks of substance abuse treatment then time to drop-out will be considered as censored at 12 weeks. Data from the TAU+TES and TAU groups will be displayed with Kaplan-Meier curves estimating the probability of retention in the CTP until time t, over time. The TAU+TES and TAU groups will be compared with a Log-Rank test stratified by site.

Assuming 50% retention at 12 weeks in TAU+TES group and 35% retention at 12 weeks in the TAU group (hazard ratio HR = log(0.35)/log(0.50) = 1.515), there is 90% power to reject H_{0-2} : HR=1.0 with the total sample size of 500 when considering two-sided α =0.025. Power is based on an unstratified log-rank test. Sample size computations were performed with the Power And Precision 2.1 package.

14.5 Interim Analyses

A DSMB will monitor the progress of the trial. In coordination with the centralized Data and Statistics Center 2, an interim check of the error variance for the primary abstinence outcome measure will be conducted to assess the adequacy of the projected study sample size. This check will not reveal the treatment effect observed in the trial at the time of this interim analysis. If the error variance is substantially different from the assumed value, there may be a need to adjust the sample size. This analysis will be conducted when approximately half participants have been enrolled and have completed the active treatment phase of the study.

Although at this time we are not planning a formal statistical interim analysis for efficacy or futility, such an interim analysis can be performed if requested by the DSMB or the sponsor. In addition, safety interim looks will be performed (without formal statistical testing) at the regular DSMB meetings or unscheduled times per the DSMB's request. If a formal interim efficacy analysis is requested, we propose to use two-sided, symmetric (O'Brien & Fleming, 1979) type boundaries generated using the flexible Lan-DeMets approach to group sequential testing (Lan & DeMets, 1983). If requested, the monitoring guidance for early stopping for futility will be based upon an approach of conditional power (Jennison & Turnbull, 2000).

14.6 Secondary Analysis of Total Number of Abstinent Half-Weeks

The secondary outcome measure of abstinence will be the total number of abstinent half-weeks. This approach is analogous to that utilized in CTN protocols #006 and #007, but using half-weeks instead of the full seven-day week. This outcome measure is simply the sum of all 24 abstinence indicators for an individual. For example, a patient could have a string of 24 half-weekly abstinence data values of 1, 1, 1, 1, 0, 0, 1, 1, 1, 0, 0, 0, 1, 1, 1, 1, 1, 1, 1, 1, 0, 0, 0, 1 where 1 denotes abstinence, and 0 drug use. This patient was abstinent in weeks 1-2, week 4, part of week 5, weeks 7-10, and the end of week 12. In this case, the total number of abstinent half-weeks is 16. Missing data will be handled in the same manner as Petry et al. (2005a). Those authors used three different methods of handling missing outcomes: (i) treat missing outcomes as being non-abstinent, (ii) treat them as abstinent, (iii) and allow them to be missing and implement an analytic method that allows for missing data. The total number of abstinent weeks will likely not be normally-distributed, but if it is then a mixed effects model can be used with fixed effects capturing the two stratification factors and indicator of treatment with TES, and a random effect capturing within site correlation. In the case of a deviation from the normality assumption, quantile regression can be used instead.

14.7 Secondary Analysis of Consecutive Half-Weeks of Abstinence

As an alternative tertiary abstinence outcome measure, at the end of the 12-week treatment we will consider the longest continuous abstinence measured in half-weeks (i.e., the largest number of consecutive half-weeks of abstinence) observed during 12 weeks of treatment. Hence, possible outcome value for a subject can be in the range between 0 and 24 half-weeks. Using these data we will compute the longest continuous abstinence. For example, considering the patient mentioned in Section 14.6, the longest continuous abstinence is 4 weeks (8 half-weeks). Missing data will be handled using the same methodology as Petry et al. (2005a). The analysis will utilize the same approach as the analysis of the total number of abstinent weeks, but with the longest continuous abstinence variable.

14.8 Other Secondary Outcome Measures

We will also evaluate secondary outcomes of (a) HIV risk behavior (using the Risk Behaviors Scale; Booth et al., 1993), (b) psychosocial functioning in areas of criminal activity, health status improvement, psychological status, family/social relationships, and employment (via the SAS-SR, Weissman, 1999, NMS, and BSI, Derogatis & Melisaratos, 1983), (c) Treatment acceptability measured via the Participant Feedback Survey (which we have successfully used in prior trials). These measures will be compared across study groups using repeated measures analyses of covariance using SAS, PROC MIXED or PROC GLIMMIX if other than normal errors are present. This procedure allows for incomplete data and varied covariance structures. We will also consider as a secondary outcome the number of abstinent half-weeks based solely on urine and breathalyzer screening (i.e. no self-report data). This outcome will be analyzed in the same way as the primary abstinence measure outcome.

14.9 Factors for Stratification

Randomization will be stratified by site and within site, by two stratifying factors: urine test positive or negative at baseline, and class of primary drug of use (stimulant vs. non stimulant). The stratification factors will be included in the analyses.

14.10 Significance testing

With various analyses (primary and secondary) proposed in this protocol, there is a multiplicity of analyses to be performed, which leads to an increased probability that at least one of the comparisons could be statistically significant by chance. Adjustment for multiplicity of testing (e.g., a Hochberg or Bonferroni approaches) for all the considered analyses would require very small p-values to declare statistical significance and is thus not feasible.

Hence, for the two pre-specified primary outcomes we consider the Hochberg approach as described in detail at the beginning of Section 14.4. In summary, this approach allows detection of treatment effect for both primary outcomes at the 0.05 level if each outcomes is significant at the 0.05 level. If either outcome is not significant at the 0.05 level, then the other will only be significant if its p-value is less than 0.025 (=0.05/2).

For the secondary analyses we will not consider significance level adjustment. However, we will be conservative in interpretation of these analyses, taking into account the degree of significance, and consistency across analyses. In addition, to guard against spurious significance results we limited and pre-specified the secondary analyses.

14.11 Demographic and Baseline Characteristics

Baseline demographic and clinical variables will be summarized for each arm of the study. Descriptive summaries of the distribution of continuous baseline variables will be presented with percentiles (median, 25th and 75th percentiles), and with mean and standard deviation.

Categorical variables will be summarized in terms of frequencies and percentages. Since randomization is expected to produce balance at baseline between the two arms of the trial, statistical comparisons of treatment groups with respect to baseline characteristics should be more informal. In case differences between treatments arms are suspected, statistical testing will be performed. For comparisons of treatment groups with respect to continuous baseline variables we will use the two sample Wilcoxon test. Group comparisons with respect to discrete baseline variables will use the chi-square test or Fisher's Exact Test as appropriate.

14.12 Gender Exploratory Analysis

We plan to conduct exploratory analyses to examine if differential outcomes are observed on the two primary outcome measures of weeks of abstinence and retention, as well as the outcome measure of intervention acceptability (based on participant feedback data), by gender. We will conclude differential treatment effect if the interaction between treatment and gender is significant at the 0.05 level.

14.13 Other Exploratory Analyses

Finally, we plan to conduct analyses to determine if differential outcomes are observed across various sub-groups (e.g., individuals whose primary drug of abuse is a stimulant vs. nonstimulant, etc.). We will also examine a variety of demographic variables, as well as baseline psychological and other history variables (e.g., comorbid psychiatric disorders), which may predict successful outcomes in reducing substance use and treatment retention. In this process, repeated measures logistic regression (abstinence) and Cox Regression (retention) will be used to examine this secondary aim of establishing whether specific measured subject characteristics at baseline are predictive of treatment outcome on these measures. Interaction tests will also be conducted to examine differential effects of predictors across each condition for each outcome measure (i.e., exploring for moderators of treatment effect). The resulting data may be important to understanding if specific sub-groups of individuals with substance use disorders may differentially benefit from the web-based intervention.

We will also consider sensitivity analysis to assess impact of the approach to dealing with missingness of abstinence data on estimated treatment effect for the primary abstinence outcome. One method we will use to evaluate our method of handling missing data is to compare it to that of Petry et al. (2005a) where a week with unknown (missing) substance use status is considered positive, i.e. probability of positive substance use is considered to be 1. Multiple imputation methods will also be used if the amount of within-subject missingness is reasonable. It is likely that the missingness mechanism involved in drug use trials is non-ignorable since a subject may not appear at their scheduled visit if they have used drugs. One method of evaluating the sensitivity of the proposed primary analysis of abstinence is to implement pattern mixture models (Hedeker & Gibbons, 1997), which are thought to deal with non-ignorable missingness more appropriately.

Sensitivity analyses will also be performed to evaluate whether the assumed model is reasonable. As previously described, we assume no treatment by time interaction after half-week 17, but we plan to relax this assumption in the planned sensitivity analyses. Another assumption we will relax is that the relationship between time and treatment effect is linear prior to half-week 17. Lastly, it is possible that using a cut-off other than week 8 is more appropriate. Methods for identifying knot locations will be used to identify how sensitive the observed results are to consideration of a different time-point where the time by treatment interaction is minimal.

After conducting all planned primary, secondary and exploratory outcome analyses, we may conduct additional analyses with data obtained in the trial, as appropriate.

14.14 Economic Analyses

We estimate and analyze incremental cost-effectiveness ratios (ICER) to inform an adoption decision from a health care sector perspective and the treatment program's perspective. The primary ICER will be the incremental costs per increased abstinence time (the clinical measure of effectiveness) and the secondary ICER will be incremental costs per increased quality adjusted life year (QALY) (the economic measure of effectiveness). We distinguish the health care perspective from the CTP perspective by the costs included in the cost-effectiveness ratio. The health care sector perspective include all medical and treatment costs regardless of the setting in which they are incurred. The CTP perspective only includes those costs that are incurred during the substance abuse treatment received within the CTP. All ICERs are assessed over 3 months and over 6 months. There are also two separate exploratory economic analyses. We assess the benefit of reduced criminal activity and use of the criminal justice system and we assess the fixed costs of program startup.

14.14.1 Estimation for Economic Analyses

- (a) Calculate Medical Costs. We calculate medical costs using the resource costing method. This method involves determining a price weight for each resource unit consumed (Brown, 1998; Gold, 1996; Glick, 1995; Drummond et al., 1991) and multiplying price weights by units of service. Price weights will be determined from the Program DATCAP described earlier and from published information. Counts of resource units are available from clinical forms within the study site for study delivered services and from the NMS form for services delivered outside the study. CTP costs are based on resources used in the treatment program and medical costs are based on all medical resources used including those used in the treatment program.
- (b) *Estimate Cost of Treatment.* The estimates of costs and cost differences between treatment groups will be expressed by use of the arithmetic mean because this summary measure permits a budgetary assessment of treatment. We will use the parametric t-test, which is the most common univariate statistical test for differences in arithmetic means. Because of the often highly skewed distribution of cost data with a long and sometimes heavy right tail, the normality assumption underlying this test may be called into question. As a result, the non-parametric bootstrap, which has the added advantage of avoiding a parametric assumption about the distribution of costs, will be used as a check on the robustness of standard parametric t-tests (Efron & Tibshirani, 1994; Desgagne et al., 1998; Barber & Thompson 2000). We will use the inverse probability weighting method proposed by Lin (2000b) to account for censored cost data.

14.14.2 Estimate Incremental Effectiveness of Treatment

The statistical model used for the primary effectiveness outcome (abstinence weeks) will be the same as described for the clinical study and the statistical model for the secondary effectiveness outcome (QALYs) will be the same as those used for costs in Section 14.14.1(b).

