14.1.2 Secondary Hypotheses

- We hypothesize that differential outcomes in drug abstinence observed across groups during treatment will continue to be observed at the 3- and 6- month follow-up time points.
- We expect that psychosocial functioning will improve in the group that received the modified TAU+TES at 3- and 6-month follow-up time points relative to the TAU alone condition.
- We hypothesize that the modified TAU+TES intervention will be cost-effective relative to TAU from both the health care sector and CTP program perspectives at the 3- and 6-month follow-up time points.
- We hypothesize that individuals in modified TAU+TES will show significant increases in coping skills acquisition (as measured via the Coping Strategies Scale) relative to TAU at end of treatment and 3- and 6-month time points, and we expect that coping skills will be shown to serve as a mediator substance use outcomes.

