Since the primary outcome of abstinence is binary and measured over the 12 weeks of the treatment phase, a longitudinal logistic regression model will be the used for the analysis. The logistic model has two components: a linear association between treatment and the log-odds of abstinence over the first 16 half-weeks, and a constant treatment effect (odds ratio) beginning at half-week 17, and extending through the end of the treatment phase. Figure 1 gives a graphical representation of this "piecewise linear" model. The intercepts α_0 and α_1 are the log-odds of abstinence in the first half-week for the TAU and TAU+TES arms respectively. β_0 and β_1 are the increase in the log-odds of abstinence across consecutive half-weeks (for *t*=1,...,16). The slope of the log-odds line after half-week 16, that is common to both treatment arms, is captured by Φ .

Letting TES_i be an indicator of whether a participant was randomized to the TAU+TES arm, the piece-wise model for all i (i=1,...,n) and t (t=1,...,24) is given by

logit $P(y_{it} = 1) = \alpha_0 (1 - TES_i) + \alpha_1 TES_i + \beta_0 (1 - TES_i) [17 + I{t < 17}(t - 17)]$

+ $β_1$ TES_i [17+I{*t*<17}(*t*-17)] + Φ I{*t*≥17}(*t*-17)

where $I{\cdot}$ is the indicator function. More simply, the logit $P(y_{it} = 1)$ can be split as follows:

[figure not shown]
t <17:
$$\alpha_0$$
 (1- TES_i) + α_1 TES_i + β_0 (1- TES_i) (*t*) + β_1 TES_i (*t*)

[figure not shown]
$$t \ge 17$$
: $\alpha_0 (1 - \text{TES}_i) + \alpha_1 \text{TES}_i + 17 \beta_0 (1 - \text{TES}_i) + 17 \beta_1 \text{TES}_i + \Phi (t-17)$

Further, we adjust for the two stratification factors. Let z_i be an indicator of whether the participant's primary drug of use is a stimulant, and x_i an indicator of whether the participant's baseline urine screen was positive. In this case the longitudinal logistic regression becomes:

$$\begin{aligned} t <& 17: \quad \gamma \ z_i + \eta \ x_i + \alpha_0 \ (1 - \mathsf{TES}_i) + \alpha_1 \ \mathsf{TES}_i \ + \beta_0 \ (1 - \mathsf{TES}_i) \ (t) + \beta_1 \ \mathsf{TES}_i \ (t) \\ t \geq& 17: \quad \gamma \ z_i + \eta \ x_i + \alpha_0 \ (1 - \mathsf{TES}_i) + \alpha_1 \ \mathsf{TES}_i \ + 17 \ \beta_0 \ (1 - \mathsf{TES}_i) \ + 17 \ \beta_1 \ \mathsf{TES}_i + \Phi \ (t-17) \end{aligned}$$

In this model the log-OR of abstinence associated with using a stimulant is captured by γ , and the log-OR associated with testing positive at baseline is denoted by η .

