14.14.3 Estimate Incremental Cost-Effectiveness Ratio

The primary ICER is estimated as the difference between mean costs of the modified TAU + TES group and the mean costs of the TAU group divided by the mean abstinence weeks of the modified TAU+TES group and the mean abstinence weeks of the TAU group. This ratio represents the additional cost of the experimental arm over TAU necessary to produce an additional drug-free week. We will estimate this ratio for both treatment costs and all medical costs. Similarly, a cost-effectiveness ratio will be estimated using QALYs in the denominator. We will estimate the cost-effectiveness ratios at 12 weeks and at 6 months. In total we will have

8 outcomes with the 4 outcomes using abstinence weeks as the denominator as the primary economic outcomes.

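### The cost-effectiveness ratio needs a difference in mean abstinent weeks, but the model named for it does not directly give one on the path the protocol expects; QALYs are compared without baseline EQ-5D

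*Protocol*

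**What the plan says.** **Abstinence denominator.** Protocol 14.14.2 states: "The statistical model used for the primary effectiveness outcome (abstinence weeks) will be the same as described for the clinical study". Two clinical analyses could be meant.

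- In 14.4.1, for the 24 half-week indicators, "a longitudinal logistic regression model will be the used for the analysis". It is fitted by GEE and has "a constant treatment effect (odds ratio) beginning at half-week 17, and extending through the end of the treatment phase".
- In 14.6, for the total number of abstinent half-weeks, a mixed model with the two stratification factors is offered if the total is normally distributed. The section expects that it will not be, and adds: "In the case of a deviation from the normality assumption, quantile regression can be used instead". It names no quantile.

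Section 14.14.3 defines the primary ratio by each arm's mean costs and mean abstinence weeks. Section 14.14.4 plans on the same scale: 2.4 against 3.6 weeks.

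**QALYs.** Section 14.14.2 sends QALYs to the cost methods of 14.14.1(b), where: "We will use the parametric t-test, which is the most common univariate statistical test for differences in arithmetic means". A bootstrap check and inverse probability weighting for censoring follow. No covariate is named. EQ-5D is measured at baseline, weeks 4, 8 and 12, and both follow-up visits (7.0, 7.3.1 and the assessment schedule).

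**Horizons.** In 14.14.3: "We will estimate the cost-effectiveness ratios at 12 weeks and at 6 months". Section 14.14 gives 3 months and 6 months. The hypothesis in 14.1.2 is cost-effectiveness "from both the health care sector and CTP program perspectives at the 3- and 6-month follow-up time points", and section 5.2 places those visits after the intervention.

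**The concern.** A cost-effectiveness ratio prices one extra unit of effect on average, so its denominator must be a difference in arithmetic means, as its numerator is. Section 14.14.1(b) argues for arithmetic means of costs because they support budgeting, and the same argument applies to abstinent weeks. An analyst who follows 14.14.2 literally arrives at an odds ratio for the last four weeks or, in the case the protocol expects, a difference in quantiles. Each must be replaced or converted before 14.14.3 can be applied, and the protocol does not say how. The choice would then be made with the data in view, for a result meant to inform adoption.

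The QALY comparison leaves baseline utility out, although it is measured and forms part of the QALY area itself. It also sits awkwardly with 14.9, which puts the stratification factors in the analyses.

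The abstinence ratio at 6 months counts among the primary economic outcomes in 14.14.3. The half-week measure in 14.2.1 exists only for the 24 half-weeks of treatment.

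**Working it through.** **1. Planning ratio on means.** Inputs from 14.14.4: costs $467 (SD 374) and $823 (SD 659); abstinent weeks 2.4 (SD 3.38) and 3.6 (SD 3.87).

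- Cost difference: 823 - 467 = $356.
- Effect difference: 3.6 - 2.4 = 1.2 weeks.
- Ratio: 356 / 1.2 = $297 per abstinent week.

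The threshold in 14.14.4 reproduces: 0.05 / 1.8 x 50,000 = $1,389, stated as $1,400.

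The stated 96% power is a separate matter and nothing below depends on it. A net-benefit calculation uses common SD 3.63, cost SD 536 (root mean square), correlation 0.15 and 250 per arm:

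z = (1,400 x 1.2 - 356) / sqrt[(2/250)(1,400² x 3.63² + 536² - 2 x 0.15 x 1,400 x 3.63 x 536)] = 1,324 / 449.9 = 2.94

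That is 83.7% power at two-sided 5%. Section 14.14.4 gives no alpha, so whether 96% reproduces cannot be settled.

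**2. What each candidate model yields.**

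| Model | Direct output | Mean weeks over 12 weeks? |
|---|---|---|
| Logistic GEE (14.4.1) | log odds ratio, half-weeks 17-24 | only if predicted probabilities are summed and averaged |
| Mixed model (14.6, if normal) | adjusted mean difference | yes |
| Quantile regression (14.6, expected case) | difference in a quantile, none named | no |

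**3. Quantile contrasts.** Assumption: abstinent half-weeks follow a beta-binomial on 24, matched to the stated means and SDs. The cost difference stays at $356.

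| Contrast | TAU | TAU+TES | Difference (weeks) | Ratio |
|---|---|---|---|---|
| Mean | 2.4 | 3.6 | 1.2 | $297 |
| 25th percentile | 0 | 0 | 0 | undefined |
| Median | 0.5 | 2.0 | 1.5 | $237 |
| 75th percentile | 4.0 | 6.5 | 2.5 | $142 |

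**4. Logistic model converted to weeks.** Assumptions: 20% abstinent at the start (14.4.1), no covariates, TAU slope on the log-odds of 0 to 0.06 per half-week, odds ratio 1.5 from half-week 17. Summing predicted probabilities over 24 half-weeks and halving gives 2.97 - 2.40 = 0.57 weeks at slope 0 and 4.78 - 4.02 = 0.77 weeks (unrounded) at slope 0.06. The conversion is possible, but the protocol does not specify it.

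**5. QALY precision.** Adjusting for baseline removes a share of variance equal to the squared correlation between baseline utility and QALY. The protocol gives no such correlation, so all values are assumed. Over 12 weeks, with measurements at 0, 4, 8 and 12, the area weights are 1/6, 1/3, 1/3, 1/6.

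| Assumption | Variance removed |
|---|---|
| Baseline-to-QALY correlation 0.3 to 0.7 set directly | 9% to 49% |
| Correlation decaying by visit, 0.4 to 0.6 between adjacent visits | 27% to 43% |
| Equal correlation 0.4 to 0.6 between all visits | 44% to 62% |

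For chance imbalance, with an assumed utility SD of 0.15 to 0.25 and 250 per arm, the standard error of the baseline difference is SD x sqrt(2/250) = 0.013 to 0.022. An imbalance of 0.02 carried through 12 weeks shifts the QALY difference by 0.02 x 12/52 = 0.0046.

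**6. Horizons.** Counted from the start of treatment, 14.14 (3 and 6 months) and 14.14.3 (12 weeks and 6 months) agree. The visits named in 14.1.2 come 3 and 6 months after a 12-week intervention, so about 6 and 9 months from the start. Twice-weekly urine stops at week 12 (7.2.1). The TimeLine Follow-Back covers the time since the last assessment at follow-up, so self-reported days are available for the later period.

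**The case against.** The strongest reply is that 14.14.3 already names arm means. A reader might infer from 14.14.2 that the ratio will divide dollars by an odds ratio or a median. The documents do not support that: the denominator is defined by means, the power section plans on means, and quantile regression is permitted rather than required. The term abstinence weeks also points to the count in 14.6, whose mixed-model branch does give an adjusted mean difference. All of this stands. What remains is that 14.14.2 does not say which model applies, and the branch the protocol expects does not produce the quantity that 14.14.3 asks for.

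A reader might also infer that the QALY analysis is biased. It is not. A difference in arithmetic means is the right target and is unbiased under randomisation, and chance imbalance is already reflected in its standard error. The loss is precision. Covariates can be left to an analysis plan, but here the protocol itself names a t-test.

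The horizon sections could be read as contradicting each other throughout. In fact 14.14 and 14.14.3 agree if counted from treatment start, and only 14.1.2 differs. Nor are data lacking after week 12, because self-report continues.

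Finally, the dollar figures rest on an assumed distribution. All the defined ratios lie well below the $920 and $1,400 in 14.14.4, so they do not show that an adoption conclusion would change.

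**Conclusion.** Sections 14.14.2 and 14.14.3 do not fit together and should be reconciled. This is an unsettled specification, not a settled wrong denominator. Under the beta-binomial assumption the choice moves the planning ratio from $297 to between $142 and $237, or leaves it undefined. Leaving baseline EQ-5D out of the QALY comparison gives up roughly 9% to 62% of variance across correlations that are all assumed, and leaves chance baseline imbalance in the estimate. The horizons need one wording, and the abstinence measure beyond week 12 needs a definition. The economic analysis is secondary, so neither co-primary clinical result is touched. The changes are still worth making because they cost little.

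**What to change.** 1. In 14.14.2, specify the adjusted difference in arithmetic mean abstinent weeks from a linear model with the stratification factors, used whether or not the data look normal. Obtain uncertainty by resampling participants, with costs and effects drawn together.
2. Estimate the QALY difference by regression on arm, baseline EQ-5D and the stratification factors. Keep the bootstrap and the censoring weights of 14.14.1(b).
3. Reconcile the horizons in 14.1.2 with those in 14.14 and 14.14.3, and state the origin from which each is counted. For any horizon beyond week 12, use abstinent weeks based on the TimeLine Follow-Back.

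The cost is revised wording and modest programming, plus reliance on self-report after week 12. No new data are needed.
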